1. Based on recommendations from FDA, the dose of hydroxychloroquine in the trial was changed from hydroxychloroquine 400 mg every 12 hours for 10 doses (version 1) to hydroxychloroquine 400 mg every 12 hours for 2 doses followed by 200 mg every 12 hours for 8 doses (version 1.1). This change was made before any patients were enrolled and before the trial was posted on clinicaltrials.gov.

Protocol Version 2.0

Date: April 14, 2020

Substantive protocol changes in Version 2.0:

1. Inclusion criterion #4 changed so that only patients with laboratory-confirmed SARS-CoV-2 infection are eligible. Patients with pending SARS-CoV-2 test results with a high clinical suspicion of COVID-19 are no longer eligible. This change was made because SARS-CoV-2 laboratory results are now routinely available within hours of initial hospital presentation at participating hospitals (which was not true early in the COVID-19 pandemic).
2. Exclusion criterion #16 was added. This exclusion criterion states that a patient is excluded if the treating clinical team does not believe equipoise exists regarding the use of hydroxychloroquine for treatment of this patient.
3. Discussion of potential drug shortages was removed because study drug for all sites will be supplied by the PETAL Network and will not rely on local drug supplies.
4. Language describing consent processes was revised to increase precision.
5. Revised the statistical considerations section (Section 7).
6. Corrected the definition of serious adverse event in section 11.1 to harmonize with section 11.3
7. Added the following statement to Appendix C: “The Medical Monitor will provide to Sandoz Pharmacovigilance any significant safety findings (without disclosing protected health information) during the conduct of the trial.”
8. Added Appendix D: Public Readiness and Emergency Preparedness Act
9. Additional data collection added: Clinically diagnosed deep vein thrombosis (DVT) or pulmonary embolism (PE)
10. Clarification of patient co-morbidities added

Protocol Version 3.0

Date: May 4, 2020

Substantive Changes in Version 3.0:

1. Operationalized the definition of shortness of breath in inclusion criteria #3.
2. Added option for attestation of signature for confirmation of informed consent (section 3.6).
3. Clarified recommendations for stopping guidelines in statistical considerations section, using an odds ratio to suggest futility of 1.1 (section 7.1).

Protocol Version 4.0

Date: June 4, 2020

Substantive Changes in Version 4.0

1. Added language for the DSMB to consider stopping the trial for harm (section 7.1): “If we determine there is >70% probability that the odds ratio is <0.70, the DSMB should consider stopping the trial for harm.”
2. Added language that enrollment will be paused after 510 participants until the DSMB reviews primary outcome data from all 510 participants.
3. Added Appendix E: The ORCHID-BUD Outcomes Related to COVID-19 treated with Hydroxychloroquine among In-patients with symptomatic Disease – Brain Outcomes and Psychological Distress Ancillary study procedures.

ABBREVIATIONS

ACE-I	Angiotensin-converting-enzyme inhibitor
ARB	Angiotensin II receptor blocker
ADR	Adverse drug reaction
AE	Adverse event
DSMB	Data safety monitoring board
eCRF	Electronic case report forms
GFR	Glomerular filtration rate
ICU	Intensive care unit
IV	Intravenous
LAR	Legally authorized representative
LFT	Liver function test
MIC	Minimum inhibitory concentration
NSAIDs	Nonsteroidal anti-inflammatory drug
PI	Principal investigator (a clinician responsible for one site)
RCT	Randomized control trial
SAE	Serious adverse events
S/F	SpO ₂ /FiO ₂ ratio
SOFA	Sequential Organ Failure Assessment
SOP	Standard operating Procedure

1. STUDY SUMMARY

Title	Hydroxychloroquine for the Early Treatment of COVID-19 in Hospitalized Adults: A Multicenter Randomized Clinical Trial
Acronym	ORCHID O utcomes R elated to C OVID-19 treated with H ydroxychloroquine among I n-patients with symptomatic D isease
Background	Effective therapies for COVID-19 are urgently needed. Hydroxychloroquine is an antimicrobial agent with immunomodulatory and antiviral properties that has demonstrated in vitro activity against SARS-CoV-2, the virus that causes COVID-19. Preliminary reports suggest potential efficacy in small human studies. Clinical trial data are needed to determine whether hydroxychloroquine is effective in treating COVID-19.
Study Design	Blinded, multicenter, placebo-controlled randomized clinical trial
Intervention group	Hydroxychloroquine 400 mg twice daily for two doses, then 200 mg twice daily for the subsequent eight doses (10 total doses)
Control group	Matched placebo twice daily for 10 total doses
Sample Size	Up to 510 patients
Inclusion Criteria	
 1. Age ≥ 18 years 2. Currently hospitalized or in an emergency department with anticipated hospitalization. 3. Symptoms of acute respiratory infection, defined as one or more of the following: 
 a. cough b. fever ($> 37.5^{\circ} \text{C} / 99.5^{\circ} \text{F}$) c. shortness of breath (operationalized as any of the following: subjective shortness of breath reported by patient or surrogate; tachypnea with respiratory rate ≥ 22 /minute; hypoxemia, defined as $\text{SpO}_2 < 92\%$ on room air, new receipt of supplemental oxygen to maintain $\text{SpO}_2 \geq 92\%$, or increased supplemental oxygen to maintain $\text{SpO}_2 \geq 92\%$ for a patient on chronic oxygen therapy). d. sore throat 4. Laboratory-confirmed SARS-CoV-2 infection within the past 10 days prior to randomization.
Exclusion Criteria	
 1. Prisoner 2. Pregnancy 3. Breast feeding 4. Unable to randomize within 10 days after onset of acute respiratory infection symptoms 5. Unable to randomize within 48 hours after hospital arrival 6. Seizure disorder 7. Porphyria cutanea tarda 8. QTc > 500 ms on electrocardiogram within 72 hours prior to enrollment 9. Diagnosis of Long QT syndrome 10. Known allergy to hydroxychloroquine, chloroquine, or amodiaquine

	
11. Receipt in the 12 hours prior to enrollment, or planned administration during the 5-day study period that treating clinicians feel cannot be substituted for another medication, of any of the following: amiodarone; cimetidine; dofetilide; phenobarbital; phenytoin; sotalol
 
12. Receipt of >1 dose of hydroxychloroquine or chloroquine in the 10 days prior to enrollment
 
13. Inability to receive enteral medications
 
14. Refusal or inability to be contacted on Day 15 for clinical outcome assessment if discharged prior to Day 15
 
15. Previous enrollment in this trial
 
16. The treating clinical team does not believe equipoise exists regarding the use of hydroxychloroquine for the treatment of this patient

Randomization	Eligible participants will be randomized 1:1 to hydroxychloroquine versus placebo. Randomization will be completed in permuted blocks of variable size and stratified by site.
Blinding	Patients, treating clinicians, trial personnel, and outcome assessors will be blinded to group assignment.
Primary Outcome	
COVID Ordinal Outcomes Scale on Study Day 15:
 
 1. Death 2. Hospitalized on invasive mechanical ventilation or ECMO 3. Hospitalized on non-invasive ventilation or high flow nasal cannula 4. Hospitalized on supplemental oxygen 5. Hospitalized not on supplemental oxygen 6. Not hospitalized with limitation in activity 7. Not hospitalized without limitation in activity
Secondary Outcomes	
 • Time to recovery, defined as time to reaching level 5, 6, or 7 on the COVID Outcomes Scale, which is the time to the earlier of final liberation from supplemental oxygen or hospital discharge • All-location, all-cause 14-day mortality (assessed on Study Day 15) • All-location, all-cause 28-day mortality (assessed on Study Day 29) • COVID Ordinal Outcomes Scale on Study Day 3 • COVID Ordinal Outcomes Scale on Study Day 8 • COVID Ordinal Outcomes Scale on Study Day 29 • Composite of death or receipt of ECMO through Day 28 • Oxygen-free days through Day 28 • Ventilator-free days through Day 28 • Vasopressor-free days through Day 28 • ICU-free days through Day 28 • Hospital-free days through Day 28
Safety Outcomes	
 • Seizure • Atrial or ventricular arrhythmia • Cardiac arrest • Elevation in aspartate aminotransferase or alanine aminotransferase to twice the local upper limit of normal • Acute pancreatitis • Acute kidney injury • Receipt of renal replacement therapy

	
 • Symptomatic hypoglycemia • Neutropenia, lymphopenia, anemia, or thrombocytopenia • Severe dermatologic reaction
Analysis	
The primary analysis will be an intention-to-treat comparison of the primary outcome between patients randomized to hydroxychloroquine versus placebo using a proportional odds model. An odds ratio (OR) >1.0 indicates more favorable outcomes with hydroxychloroquine on the COVID Ordinal Outcome scale, while an OR <1.0 indicates more favorable outcomes with placebo. The trial is designed with a Bayesian monitoring plan and has an anticipated sample size around 510 patients. The suggested stopping boundaries for the DSMB to consider include: >95% probability that the OR is >1.0 with a skeptical prior distribution (stop for efficacy); >90% probability that the OR is <1.1 with a flat prior (stop for futility); or >70% probability that the OR is <0.7 with a flat prior (stop for harm). With 5 interim analyses, a simulation showed that over 90% of trials would show efficacy on or before the fifth interim analysis (510 patients) if the true odds ratio were 1.8. Meanwhile, 6% of trials would show efficacy, and 77% would stop for futility if the odds ratio were 1.0. If the trial enrolls 510 participants, further enrollment will be paused until the DSMB reviews data on the primary outcome from all enrolled participants; a decision to continue enrollment will be made by NHLBI after reviewing DSMB recommendations while the investigators remain blinded.

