We plan to use a Bayesian analysis of the evolving data which allows flexibility in the number and timing of the interim analyses. If we determine there is >95% probability of the odds ratio being >1.0, the DSMB should consider stopping the trial for efficacy. If we determine there is >90% probability that the odds ratio is <1.1, the DSMB should consider stopping the trial for futility. If we determine there is >70% probability that the odds ratio is <0.70, the DSMB should consider stopping the trial for harm. We will use a prior odds ratio of 1.0 (equal chance of harm and benefit; mean log OR of 0.0) and a prior distribution of the standard error for its log set at 0.352 for tests of efficacy and a non-informative prior for tests of futility and harm. The results will be reported in a similar manner to those published by Goligher et al.³⁶ One advantage of Bayesian analysis is that stopping guidelines are not binding and the DSMB is charged with using judgement and data both internal and external to the trial to make any irrevocable decision.

If the trial enrolls 510 participants, further enrollment will be paused until the DSMB reviews data on the primary outcome from all enrolled participants; a decision to continue enrollment will be made by NHLBI after reviewing DSMB recommendations while the investigators remain blinded.

We calculated probabilities that this trial would stop for efficacy or futility based on several fixed scenarios assuming we had an interim analysis after each 102 patients. The probabilities for continuing, stopping for efficacy, and stopping for futility based on a true odds ratio of 1.0 (no difference between the hydroxychloroquine and placebo groups) and 1.8 (substantially better outcomes in the hydroxychloroquine group) are show in Table 2 and Table 3.

Table 2. Probabilities of continuing or stopping the trial before or at the time 510 patients analysed based on a true odds ratio of 1.0 and 1.8.		
	Odds Ratio = 1.0 Probability	Odd Ratio = 1.8 Probability
Continue	0.556	0.057
Stop for Efficacy	0.061	0.937
Stop for Futility	0.383	0.007

Table 3. Probabilities of continuing or stopping the trial on or before the n^{th} interim analysis based on a true odds ratio of 1.0 and 1.8.						
Interim Analysis	Odds Ratio = 1.0			Odds Ratio = 1.8		
	Continue	Stop for Efficacy	Stop for Futility	Continue	Stop for Efficacy	Stop for Futility
1	0.844	0.006	0.150	0.840	0.154	0.006
2	0.744	0.021	0.235	0.494	0.500	0.007

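### The protocol synopsis says 77% of trials stop for futility under no effect; the protocol's own tables and a simulation of the stated rule give 38%

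*Protocol*

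**What the plan says.** The Analysis row of the protocol's Study Summary lists the suggested stopping boundaries, including ">90% probability that the OR is <1.1 with a flat prior (stop for futility"). It then reports the simulated performance: "With 5 interim analyses, a simulation showed that over 90% of trials would show efficacy on or before the fifth interim analysis (510 patients") at a true odds ratio of 1.8, followed by "Meanwhile, 6% of trials would show efficacy, and 77% would stop for futility if the odds ratio were 1.0".

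Protocol section 7.1 states the same rule: "If we determine there is >90% probability that the odds ratio is <1.1, the DSMB should consider stopping the trial for futility". The efficacy rule is "If we determine there is >95% probability of the odds ratio being >1.0, the DSMB should consider stopping the trial for efficacy", and the priors are "a prior distribution of the standard error for its log set at 0.352 for tests of efficacy and a non-informative prior for tests of futility"; the harm rule uses the same flat prior. With a look after every 102 patients, the Table 2 futility row reads "Stop for Futility 0.383 0.007" for true odds ratios of 1.0 and 1.8. The last row of Table 3 gives, at an odds ratio of 1.0, 0.556 continuing, 0.061 efficacy and 0.383 futility.

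SAP section 4.3 repeats the thresholds but gives no operating characteristics.

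**The concern.** The protocol gives two answers to one question. The synopsis figures of 6% (table 0.061) and over 90% at an odds ratio of 1.8 (table 0.937) agree with section 7.1. Only the 77% does not.

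This figure tells a reader how readily the trial would stop if the drug did nothing. At 77%, an ineffective drug is dropped by 510 patients in about three trials out of four. At 38%, most such trials reach 510 without a conclusion. That bears on how many patients are expected to be studied if there is no effect, and on how informative a null trial is likely to be. It also bears on the claim in protocol section 9.1.2 that the design keeps enrolment to the minimum needed. The error is in the favourable direction, in the part of the protocol most likely to be read alone.

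**Working it through.** **Inputs.** Looks every 102 patients (51 per arm), five looks, 1:1 allocation. Day 15 distribution from protocol Table 1: 11.5%, 5.8%, 21.9%, 60.8%. Efficacy prior for the log odds ratio N(0, 0.352²); flat prior for futility and harm. The standard error (SE) per look is not printed, so it is derived here and then varied.

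**Standard error at the first look.** Under proportional odds with equal arms the information is I₁ ≈ (N/12)(1 − Σp³).

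- Σp³ = 0.115³ + 0.058³ + 0.219³ + 0.608³ = 0.237
- I₁ = (102/12)(0.763) = 6.486, so SE = 1/√6.486 = 0.393
- The finite-sample form, n₁n₂N/[3(N+1)²] × (1 − Σp³), gives 6.360 and SE = 0.3965

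At look k the SE is SE₁/√k.

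**Boundaries on the estimated log odds ratio x, with SE s.**

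- Futility: x < log(1.1) − 1.2816 s
- Efficacy: x/s > 1.645 √(1 + s²/0.352²)
- Harm: x < log(0.70) − 0.5244 s

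**Hand check at look 1, true odds ratio 1.0, s = 0.393.** The futility probability is Φ(0.0953/0.393 − 1.2816) = Φ(−1.039) = 0.149. Table 3 has 0.150.

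**All five looks, by simulation.** Score increments were drawn as N(log OR × I₁, I₁), with one to four million trials per run. Cumulative futility at a true odds ratio of 1.0:

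| Look | Protocol Table 3 | SE 0.3965 | SE 0.393 |
|---|---|---|---|
| 1 | 0.150 | 0.149 | 0.149 |
| 2 | 0.235 | 0.235 | 0.237 |
| 3 | 0.297 | 0.297 | 0.299 |
| 4 | 0.344 | 0.345 | 0.347 |
| 5 | 0.383 | 0.384 | 0.387 |

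At look 5, efficacy is 0.061 to 0.062 (table 0.061) and continuing 0.551 to 0.554 (table 0.556). At a true odds ratio of 1.8, efficacy is 0.941 to 0.944 (table 0.937). The method therefore reproduces the tables, and 77% does not follow from the stated rule.

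**Could some variant give 77% by 510 patients?**

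- SE from 0.35 to 0.45: futility 0.408 down to 0.366.
- Sceptical prior used for futility as well: 0.344.
- A single look at 510: Φ(−0.739) = 0.23.
- Harm rule added ("If we determine there is >70% probability that the odds ratio is <0.70, the DSMB should consider stopping the trial for harm"): with s = 0.40 at look 1, the harm cut-off is −0.57 and the futility cut-off −0.42. At look 5 they are −0.45 and −0.13. Harm lies inside futility at every look, so it relabels stops and adds none: 0.302 futility + 0.085 harm = 0.387.
- Continuing past 510 under the same rule: 0.77 is reached only at about 4,080 patients (40 looks), where efficacy is 0.166, not 0.06.
- A looser rule can reach it. With the 90% cut-off and flat prior kept, a threshold near 1.355 gives 0.770, and an odds ratio below about 1.3 at 85% comes close. Neither document states such a rule.

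**Consequences at an odds ratio of 1.0.** No boundary crossed at 510: 0.556 in Table 3, against 100 − 77 − 6 = 17% implied by the synopsis. Expected number analysed, from the Table 3 continuation column: 102 × (1 + 0.844 + 0.744 + 0.667 + 0.606) = 102 × 3.861 ≈ 394.

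**The case against.** The best reply concerns weight. One number in a summary row is wrong. The rule is the same in the synopsis, section 7.1 and SAP section 4.3, the tables follow from it, and the boundaries are advisory. The DSMB reviews the whole protocol, which contains the correct tables, and the synopsis itself goes on to describe the pause at 510. No estimate, threshold or sample size depends on the 77%. All of that is true: the harm is confined to readers of the synopsis. It does not make the sentence right.

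Three qualifications also stand:

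- The pause applies to any trial that enrols 510 patients, whether or not a boundary is crossed at the fifth look. The matching Table 3 figure is 0.606 (continuing after look 4). The 0.556 is the chance that no boundary has been crossed at 510.
- The 394 counts patients analysed at the stopping look. The outcome is read at Day 15, and the protocol describes a pause only at 510, so the number exposed would be larger by an amount that depends on accrual, which the documents do not give.
- The tables report only efficacy and futility. The 38% includes trials that would also meet the harm rule.

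**Conclusion.** The concern holds. The synopsis overstates the probability of a futility stop under no effect by a factor of two: 77% against 38.3% in Tables 2 and 3 and 38.4% to 38.7% by simulation. The chance of reaching 510 patients with no boundary crossed is about 56%, not the 17% implied. The contradiction can be read from the protocol without any model. The simulation is needed only to show which figure is wrong, and that result does not depend on the unprinted SE anywhere between 0.35 and 0.45. The documents do not say where the 77% came from. Because a headline operating characteristic is wrong in current text and takes one sentence to correct, it should be corrected.

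**What to change.** In the Analysis row of the Study Summary, replace 77% with 38%, and add that about 56% of trials would reach 510 patients with no boundary crossed, citing Tables 2 and 3. State that the 38% counts every crossing of the odds-ratio-below-1.1 boundary, including crossings that also meet the harm rule. If 77% was the intended property, say plainly that the stated rule (odds ratio below 1.1 with more than 90% probability, flat prior) does not deliver it.

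The cost is one sentence in the synopsis and a less favourable figure. Section 7.1, the SAP and the conduct of the trial need no change.

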2. TRIAL DESCRIPTION

2.1 Background

Coronavirus Disease 2019 (COVID-19) is an acute respiratory infectious illness caused by *severe acute respiratory syndrome coronavirus 2* (SARS-CoV-2).^{1,2} Although the epidemiology has not been fully elucidated, most adults with COVID-19 appear to experience fever, cough, and fatigue and then recover within 1-3 weeks. However, a portion of adults with COVID-19 develop severe illness, typically manifesting as pneumonia and hypoxemic respiratory failure, with continued progression to acute respiratory distress syndrome (ARDS) and death in some cases.¹⁻³ Currently, no therapies have been demonstrated to prevent progression of COVID-19 to severe illness. Based on mechanism of action and early clinical experiences, several agents currently available in the United States (US) have been proposed as potential therapies to prevent progression.⁴⁻⁶ Among these potential therapies, hydroxychloroquine has generated substantial interest due to its antiviral and immunomodulatory activity and established safety profile. In fact, many US hospitals are currently recommending hydroxychloroquine as first-line therapy for hospitalized patients with COVID-19 despite extremely limited clinical data supporting its effectiveness. Thus, data on the safety and effectiveness of hydroxychloroquine for the treatment of COVID-19 are urgently needed to inform clinical practice. In this trial, we will evaluate the safety and effectiveness of hydroxychloroquine for the treatment of adults hospitalized with COVID-19.

2.1.1 COVID-19 Infection

COVID-19 was first identified as a cluster of cases of pneumonia among a group of workers from a seafood wholesale market in Wuhan, China in December 2019.⁷ This observation, along with subsequent viral genotyping showing significant genetic similarities to the bat coronaviruses⁸ suggest a zoonotic origin, although the specific reservoir and intermediary species remain unclear.⁹ The COVID-19 infection represents the seventh coronavirus known to cause disease in humans.¹⁰ Four of the coronavirus viruses are known to cause symptoms of the common cold in immunocompetent individuals while two others (SARS-CoV and MERS-CoV) have caused recent outbreaks of severe and sometimes fatal respiratory diseases.¹¹ SARS-CoV-2 appears to exploit the same cellular receptor as SARS-CoV and MERS-CoV,¹² and its severity may similarly result from a predilection for intrapulmonary epithelial cells over cells of the upper airways.^{13,14}

Since the first documented human case, COVID-19 has spread exponentially with 216,846 confirmed cases and 8,908 deaths as of March 18, 2020. While most patients recover after a mild, brief illness with fever and cough, the disease has a clinical spectrum ranging from asymptomatic infection¹⁵ to ARDS and death.¹⁶ The most common reasons for ICU care are respiratory failure and ARDS, with a minority developing shock and possibly cardiomyopathy.¹⁷ The case fatality rate is estimated to be 0.25% to 3.0%.¹⁸

2.1.2 Hydroxychloroquine as a Therapeutic for COVID-19

Hydroxychloroquine is a medication approved by the US Food and Drug Administration and accounts for millions of US prescriptions annually. It is used both as an antiparasitic agent for malaria and an immunomodulatory agent for rheumatologic diseases. When used for short periods, hydroxychloroquine is generally well-tolerated, with the most common side effects including nausea, vomiting, diarrhea, rash, and headache. Mechanisms of action include: 1) immunomodulation: decreased inflammatory response

via inhibition of IL1, IL6, and tumor necrosis factor and impairment of complement-dependent antigen-antibody reactions; 2) antimalarial: increasing pH of the vacuole within malaria parasites preventing normal growth and replication; and 3) antiviral: increasing endosomal pH, which limits virus-cell fusion and interferes with glycosylation of cell receptors targeted by coronaviruses.^{4,5,19,20} Recent laboratory studies demonstrate that hydroxychloroquine is a potent inhibitor of SARS-CoV-2 *in vitro*.^{4,5,21} Based on these laboratory data and case series of clinical experiences, hydroxychloroquine has been proposed as a potential therapeutic for treatment of COVID-19.²²

